#### **9.1.4.7 Use of rescue medications for hyperglycemia**

The use of rescue medications for hyperglycemia will be assessed and reported throughout the 104 weeks of double-blind treatment. Routine alerts on FPG and/or HbA1c will be sent to the Investigator from the central laboratory to ensure that glycemic parameter results remain within predefined thresholds. For details and further actions should FPG values fall above thresholds, refer to [Section 8.2.2](#).

## **9.2 SAFETY ENDPOINTS**

Assessments for safety include AEs, SMBG, clinical laboratory assessments, physical examination, ECG, weight, and vital signs. An independent DMC will meet on a regular basis to review accumulating clinical trial safety data by treatment.

Adjudication of all deaths, MACE and other selected CV events, selected renal events, bone fracture, and DKA will be performed in a blinded manner by a CEC. Further details are available in [Section 6.4.3](#) and in the CEC Charter.

An expert committee will review all potential cases of DILIs in a treatment-blinded manner to evaluate causality.

The following safety endpoints will be assessed throughout the 104 weeks of double-blind treatment:

- Adverse events, hypoglycemia (all, severe, and/or documented symptomatic hypoglycemia), EOSI, adverse events of special interest (AESI), AEs leading to discontinuation of IMP, SAEs, and deaths.
- Percent change from Baseline to Weeks 26, 52 and 104 in BMD (lumbar spine, total hip, and femoral neck).
- Proportion of patients with adjudicated bone fractures over 104 weeks.
- Proportion of patients with  $\geq 3\%$  decline in BMD at Week 104.
- Changes from Baseline in bone turnover markers to Week 26, 52, and 104 (serum bone resorption markers: N-terminal telopeptide of Type 1 collagen [NTX] and  $\beta$ -CTX-1; serum bone formation markers: P1NP and osteocalcin).
- Changes from Baseline in markers of calcium metabolism to Week 26, 52, and 104 (serum: calcium, phosphorus, magnesium, parathyroid hormone [iPTH], 25-hydroxyvitamin D and 1,25-dihydroxyvitamin D; urinary: calcium, phosphorus and magnesium).

Clinical laboratory results (see [Section 9.2.1.4](#)), vital signs results, and 12-lead ECG.

### **Observation period of safety endpoints**

The observation period of safety data will be divided into 3 segments:

- The pretreatment period is defined as the time between the date of the informed consent and the first dose of double-blind IMP.
- The treatment-emergent period (TEAE period) is defined as the time from the first dose of double-blind IMP up to 10 days (1 day for hypoglycemia) after the last dose of double-blind IMP, regardless of the introduction of rescue therapy. The 10-day interval is chosen based on the half-life of the IMP (approximately 5 times the half-life of sotagliflozin in patients with moderate renal dysfunction).
- The post-treatment period is defined as the time starting 11 days after the last dose of double-blind IMP (after the treatment-emergent period).

The Baseline value for safety endpoints in the safety population is the last available value prior to the first administration of the double-blind IMP.

## **9.2.1 Assessment methods of safety endpoints**

### **9.2.1.1 Bone mineral density**

Change in BMD at lumbar spine, total hip, and femoral neck will be assessed in all patients using DXA. Baseline DXA scans for BMD assessment will be performed during Run-in (between Week -2 [Visit 2] and Baseline [Visit 3]) and centrally reviewed to confirm eligibility. To assess percent change from Baseline in BMD, post-Baseline DXA scans will be performed within 2 weeks prior to the on-site visits at Week 26 (Visit 8), Week 52 (Visit 10), and Week 104 (Visit 13). In exceptional situations, if justified based on Investigator's assessment, the DXA scan can be performed up to a maximum of 7 days after the scheduled visit. All BMD assessments will be performed locally with central review. The DXA scanners will be calibrated and monitored using phantoms provided by the central image review facility. Detailed guidance on acceptable DXA scanners and scanning procedures will be provided by the central review facility to the DXA operating sites. Sites will forward scans to the central image review facility on an ongoing basis for quality control, data validation, and imaging review. All scans will be archived onto digital media at the site and forwarded to the central image review facility within 24 hours of acquiring the scan. The site is also required to maintain a copy of the data. All DXA scans will be retained as source data. Details of DXA measurement and data analyses will be included in a separate protocol for DXA imaging provided by the central image review facility.

### **9.2.1.2 Adverse events**

Adverse events including SAE, AESI, and EOSI will be assessed. Refer to [Section 10.4](#) to [Section 10.7](#) for details.

#### **9.2.1.2.1 Adverse events of special interest**

Adverse events of special interest are listed in [Section 10.4.1.3](#) reporting requirements for AESI are presented in [Section 10.4.4](#).

#### **9.2.1.2.2 Events of special interest**

Events of special interest are separate from AESI. For a list of events defined as EOSI and their reporting requirements see [Section 10.4.1.3](#) and [Section 10.4.4](#), respectively.

### **9.2.1.3 Hypoglycemia**

Hypoglycemia events (all, severe and/or documented symptomatic hypoglycemia) will be assessed starting with signing of the ICF until 2 weeks after the last dose of IMP (**Note:** for patients who discontinue treatment before Week 104, safety data will be collected until scheduled study end). Patients will also complete the patient diary, which will be regularly reviewed by Investigators. See [Section 10.6.1](#) for further details.

### 9.2.1.4 Laboratory safety variables

The clinical laboratory data consist of blood analysis (including clinical chemistry, hematology amylase lipase, fasting lipid profile, and additional evaluations) and urinalysis, according to the schedule presented in Section 1.2. Clinical laboratory values will be evaluated after conversion into standard international units. International units will be used in all listings and tables. Table 2 lists the blood analysis parameters to be assessed by the central laboratory. Urinalysis parameters are presented in Section 9.2.1.5.

Serum FSH and estradiol will be measured in women at Screening (Visit 1, Week -4) to confirm menopausal status as needed. A postmenopausal state is defined as no menses for >12 months without an alternative medical cause. An FSH level in the postmenopausal range (>40 IU/L) may be used to confirm a postmenopausal state in women not using hormonal replacement therapy. For hysterectomized women, determination of menopausal status will be based on history of vasomotor symptoms, or FSH >40 IU/L and estradiol levels on postmenopausal range (<20 pg/mL).

**Table 2 - Blood safety parameters**

Clinical chemistry	Hematology	Other parameters
Sodium	Complete blood count (CBC)	Fasting lipid profile
Potassium	Differential white blood count (WBC)	Total cholesterol (TC)
Chloride	Platelet count	High-density lipoprotein cholesterol (HDL-C)
Carbon dioxide (bicarbonate)	Hemoglobin	Low-density lipoprotein cholesterol (LDL-C) b
Blood urea nitrogen (BUN)	Hematocrit	Non-HDL-C c
Creatinine (for eGFR calculation a )	Erythrocyte count	Triglycerides (TG)
Glucose (serum)		
Alanine aminotransferase (ALT)		Other tests
Aspartate aminotransferase (AST)		Amylase
Total bilirubin (TB)		Lipase
Alkaline phosphatase (ALP)		
Uric acid		Markers of bone and calcium metabolism
Phosphorus d		25-hydroxyvitamin D
Calcium d		1,25-dihydroxyvitamin D
Magnesium d		Parathyroid hormone (iPTH)
Total protein		Markers of bone resorption: NTX, β-CTX-1
Albumin		Marker of bone formation: P1NP, osteocalcin
Creatine phosphokinase (CPK)		
Lactic acid dehydrogenase (LDH)		

Clinical chemistry	Hematology	Other parameters
Abbreviations: ALP = alkaline phosphatase, ALT = alanine aminotransferase, AST = aspartate aminotransferase, BUN = blood urea nitrogen, CBC = complete blood count, CPK = creatine phosphokinase, eGFR = estimated glomerular filtration rate, HDL-C = high-density lipoprotein cholesterol, IDMS = isotope dilution mass spectrometry, iPTH = parathyroid hormone, LDH = lactic acid dehydrogenase, LDL-C = low-density lipoprotein cholesterol, MDRD = Modification of Diet in Renal Disease, NTX = N-terminal telopeptide of Type 1 collagen, P1NP = Type 1 procollagen N-terminal propeptide, SI = Standardized International, TB = total blood, TC = total cholesterol, TG = triglycerides, US = United States, WBC = white blood count, $\beta$ -CTX-1 = beta C-terminal telopeptide of Type 1 collagen.		
All assessments to be performed by central laboratory. All assessments measured in serum.		
a The eGFR will be calculated. The recommended equation for estimating eGFR from serum creatinine is the 4-variable MDRD (32) Study equation. The IDMS-traceable version of the MDRD Study equation will be used. Either equation below may be used based on whether the laboratory reports conventional units or SI units. Conventional Units (for use predominantly in the US): http://nkdep.nih.gov/lab-evaluation/gfr-calculators/adults-conventional-unit.asp . SI Units (for use predominately outside the US): http://nkdep.nih.gov/lab-evaluation/gfr-calculators/adults-SI-units.asp .		
b LDL-C will be calculated by Friedwald equation.		
c Non-HDL-C will be calculated as the difference between TC and HDL-C.		
d Serum calcium, phosphorus, and magnesium are also part of the panel of markers of bone and calcium metabolism.		

### 9.2.1.5 Urinalysis

Urinalysis (urine dipstick with microscopy) will be performed by central laboratory at Screening (Visit 1), Baseline (Visit 3), Week 26 (Visit 8), and Week 52 (Visit 10) and Week 104 (Visit 13). The central laboratory urinalysis includes:

- Urine dipstick includes: specific gravity, pH, protein, blood, ketones, bilirubin, urobilinogen, nitrite, and leukocyte esterase.
- Urine microscopy includes, but is not limited to: detection of formed cellular elements, casts, bacteria, yeast, parasites, and crystals in centrifuged urine sediment.

To prevent partial unblinding, the central laboratory urinalysis dipstick will not include the measurement of urine glucose.

In the event of abnormal urinalysis findings suspicious of UTI, urine culture should be performed. Positive urine culture determination will be based upon the criteria of the reporting laboratory. Additionally, urine cultures should be performed if at any point the Investigator suspects the presence of a UTI.

In addition, urine albumin, calcium, phosphorus, magnesium, and creatinine will be assessed by 24-hour urine collection at Baseline (Visit 3), Week 26 (Visit 8), Week 52 (Visit 10), and Week 104 (Visit 13). See [Section 9.1.4.5](#) for information on 24-hour urine collection.

If the urine dipstick is positive for blood, the central laboratory will perform reflexive testing to include microscopy. Additional testing will be performed according to the judgment of the Investigator. Referral to urology/urologic evaluation is recommended for new or unexplained cases of confirmed hematuria (urology/urologic evaluation is not required where hematuria is considered to be related to diabetic nephropathy).

### **9.2.1.6 Vital signs and physical examination**

Vital signs, including sitting BP and HR, will be assessed at all study visits for safety and efficacy endpoints. Full details and directions for the measurement of BP and HR are presented in [Appendix C](#). Physical examinations will be performed at every study visit.

A complete physical examination will be performed at Screening (Visit 1), Week 26 (Visit 8), and Week 104 (Visit 13). An abbreviated physical examination will be performed at all the other visits, including the Follow-up Visit/Week 106 (Visit 14). The abbreviated physical examination should focus on cardiac and respiratory systems, as well as any areas important for assessment of AEs, if necessary. The complete physical examination will also include recording of BW and vital signs. Body weight measurements are discussed in [Section 9.1.4.4](#). Height will be measured only at Screening Visit, Week 52, Week 104, and Premature EOT Visit.

### **9.2.1.7 Electrocardiogram variables**

Twelve-lead ECG recording will be performed locally at the Run-in Visit (Visit 2), and at Week 26 (Visit 8), and Visit 13 (Week 104).

The 12-lead ECG should be performed after the patient has spent at least 10 minutes in supine position and prior to IMP administration. The Investigator should review the ECG trace and document the interpretation, sign and date the ECG print out, and report the interpretation in the eCRF. Each subsequent ECG trace will be analyzed in comparison to the Run-in Phase (Visit 2) Screening ECG trace. All original ECG traces are retained as source data.

The ECG results will be evaluated as “normal” or “abnormal”.

**Note:** Any new ECG abnormality should be re-reviewed for confirmation and reported as appropriate for that finding.

### **9.2.1.8 Self-monitored blood glucose**

A meter for the self-assessment of blood glucose will be dispensed at the Run-in Visit (Visit 2). Patients will receive a patient diary at each visit except for Screening Visit (Visit 1) and Follow-up Visit (Visit 14, Week 106). The patient will enter SMBG levels into this diary. The diary will be collected and reviewed at all visits starting from the Baseline Visit (Visit 3).

Patients will be requested to self-assess blood glucose levels in the fasted state and whenever they experience any illnesses (eg, cold, flu), or symptoms of hyperglycemia or hypoglycemia. Symptoms of hypoglycemia may include shakiness, dizziness, sweating, hunger, headache, pale skin color, sudden moodiness or behavior changes (such as crying for no apparent reason), clumsy or jerky movements, seizure, difficulty paying attention or confusion, or tingling sensations around the mouth. Patients will be instructed to record the presence or absence of hypoglycemic episodes or hypoglycemic symptoms in the patient diary provided.

Patients will also be instructed to record SMBG values that are  $\leq 70$  mg/dL ( $\leq 3.9$  mmol/L) in the patient diary.

Patients should be instructed to contact the site in case 3 consecutive fasting SMBG values are:

- >270 mg/dL (15.0 mmol/L) from Baseline visit (Visit 3, Day 1) to Visit 5 (Week 6), inclusive.
- >240 mg/dL (13.3 mmol/L) from Visit 5 (Week 6) to Visit 6 (Week 12), inclusive.
- >200 mg/dL (11.1 mmol/L) from Visit 6 (Week 12) up to Visit 8 (Week 26), inclusive.
- >170 mg/dL (9.4 mmol/L) from Visit 8 (Week 26) up to Visit 10 (Week 52), inclusive.
- >160 mg/dL (8.9 mmol/L) from Visit 10 (Week 52) up to the EOT Visit 13 (Week 104).

Patients will be recommended to self-assess fasting blood glucose levels at least once a week during the study.

### 9.3 OTHER ENDPOINTS

[REDACTED]

[REDACTED]

[REDACTED]

[REDACTED]

[REDACTED]

[REDACTED]

[REDACTED]

[REDACTED]

## 9.4 APPROPRIATENESS OF MEASUREMENTS

Sotagliflozin therapy in patients with T2D who have inadequate glycemic control with a stable antidiabetic therapy is expected to lower HbA1c over 26 weeks of treatment (primary efficacy analysis). Sotagliflozin treatment for 26 weeks is likely to be of sufficient duration to observe effects on reduction of HbA1c, and is, therefore, selected as the time point for assessment of the primary endpoint HbA1c. The length of the study is considered appropriate for detection of the primary endpoint given the power estimates. The double-blind controlled extension up to 104 weeks will provide additional long-term data on efficacy and safety, including long-term assessment of bone safety with sotagliflozin treatment.

The concentration of HbA1c reflects the glycemic history of the previous 120 days and is thus an index of mean glycemia, documenting glycemic control over the past 2 to 3 months. Hemoglobin A1c has also been shown to correlate with the development of long-term complications of diabetes, and reduction of HbA1c is known to reduce the risk of long-term microvascular complications. Therefore, HbA1c is considered an appropriate primary endpoint for assessing the effect of a treatment on glycemic control. The duration of study treatment (26 weeks for the primary HbA1c endpoint) is considered to be sufficient for achieving stable conditions with IMP and for enabling an adequate assessment of time-dependent changes in HbA1c.

Improvements in FPG have been observed with sotagliflozin in multiple studies. Therefore assessment of FPG is relevant in this study. This parameter is also considered by regulatory agencies to be supportive of efficacy of an antidiabetic agent.

The problem of weight gain in T2D is widely recognized. More than 80% of individuals with T2D are overweight, many at the time of diagnosis. Consequently, iatrogenic weight gain is not only unwelcome, but represents an important clinical issue that can become a barrier to the successful management of glycemic control. Treatment with sotagliflozin is expected to result in weight loss based on the mechanism of action. Therefore, in this study, assessing change in BW from Baseline to Week 26 is a secondary endpoint.

Potential therapeutic effect of sotagliflozin on BP reduction will be assessed in all trial patients. To avoid confounding factors, modification of antihypertensive medications is not allowed during the first 12 weeks of the Treatment Period. The beneficial effect of sotagliflozin to patients with inadequately controlled hypertension (patients with Baseline SBP  $\geq$ 130 mmHg or Baseline DBP  $\geq$ 80 mmHg) will be assessed, but also the impact of sotagliflozin in the BP of normotensive patients (patients with Baseline SBP <130 mmHg or Baseline DBP <80 mmHg) will also be assessed. Given the mechanism of action of sotagliflozin on renal tubular absorption of glucose and sodium, it is appropriate to assess the impact on calcium metabolism. For this reason, specific biomarkers for calcium metabolism and bone turnover will be assessed at several time points.

Decreases in bone mass measured by BMD have been reported with canagliflozin treatment and assessment of BMD changes will be a key safety endpoint for this study. The assessment of impact of treatment on bone mass will be performed by evaluation of BMD T-scores initially after 26 weeks of treatment to enable early detection of a bone safety signal and followed out yearly after the beginning of treatment. This duration of follow-up is appropriate to detect longitudinal trends in changes in bone mass in this population that is vulnerable to development of age-related bone loss.

Alterations in calcium homeostasis have been noted in nonclinical studies with selective SGLT2 inhibitors. Changes in calcium and bone biomarkers were evaluated in diabetic patients in Study LX4211.202, and no clinically significant changes on these parameters were observed. However, as changes in bone biomarkers have been observed in clinical studies of other selective SGLT2 inhibitors, the Sponsor will continue to evaluate bone biomarkers and events of fractures in the sotagliflozin clinical program.

It is recognized that weight loss is associated with reduction in bone mass and also reduction of estradiol levels in postmenopausal women. This study will include assessment of body composition to allow evaluation of differential changes in total body fat mass versus lean mass during the treatment. The change in levels of estradiol in women will be also assessed as adipose tissue is a major source of estradiol in postmenopausal women and decrease in these levels can be implicated in changes in bone turnover.

The other efficacy and safety assessments in this study are standard and well-established measurements for a Phase 3 study evaluating the treatment of T2D in adult patients.

Safety analyses focusing on the TEAE include occurrences with SAE, AESI, EOSI, AE leading to IMP discontinuation, and hypoglycemic events. Other standard safety parameters such as vital signs, ECG and laboratory measurements will also be evaluated. The other efficacy and safety assessments in this study are standard, well-established measurements for a Phase 3 study evaluating the treatment of T2D in adult participants.

## 10 STUDY PROCEDURES

### 10.1 VISIT SCHEDULE

The visit schedule and procedures/assessments are listed in the Study Flow Chart ([Section 1.2](#)). The aim of this section is to provide details on how some of the procedures/assessments should be performed.

This is an out-patient study and consists of 14 on-site visits. Additional on-site visits or telephone contacts can be scheduled at any time during the study whenever considered necessary by the Investigator.

The patients need to arrive at the study site in a fasting state for Visit 1, Visit 3, Visit 4, Visit 5, Visit 6, Visit 8, Visit 10, Visit 12, Visit 13, and Visit 14 unless instructed otherwise by the investigator. Throughout the study, “fasting” is defined as at least 8 hours without food (no food or liquid intake, other than water). **Note:** If the patient is not fasting at the visits specified above, the blood sample will not be collected and a new appointment should be given to the patient for the following day if possible, with instruction to be fasted. Other procedures can be performed as scheduled. All laboratory assessments will occur prior to IMP and NIMP administration on the day of the visit.

The Run-in Visit (Visit 2) can be performed up to 2 weeks ( $\pm 3$ ) days after the Screening Visit and once the results of all Screening tests are available and the patient is confirmed to be eligible for participation in the study. The visit windows for the Double-blind Treatment Period visits will be as follows: Visit 3 through Visit 8 should occur at the schedule  $\pm 3$  days; Visit 9 through Visit 12 should occur at the schedule  $\pm 7$  days. Visit 13 should occur at the schedule  $\pm 3$  days and Follow-up Visit (Visit 14) should occur within 2 weeks after last dose of IMP  $\pm 3$  days.

If one visit date is changed, the next visit should occur according to the original schedule, ie, calculated from the date of Baseline visit (Visit 3, Week 0).

For a complete list of procedures scheduled for each study visit please refer to the Study Flow Chart ([Section 1.2](#)), which details the procedures to be performed.

All data obtained during the study visits are reviewed by the Investigator and Sub-investigators who are qualified in treatment of T2D and are trained on the study.

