- d Vital sign measurements (sitting BP and HR): 3 separate seated BP and HR measurements should be taken with at least 1 minute between readings, following a 5-minute rest period and prior to phlebotomy (see Appendix C).
- e The abbreviated physical exam should focus on cardiac and respiratory systems, as well as any areas important for assessment of AEs if necessary.

- f* Patients will be instructed to measure their fasting glucose levels via SMBG and discuss results with site personnel at clinic visits or phone contacts. The frequency of the fasting SMBG measurements will be determined by the Investigator according to the clinical need and background diabetes treatment, but it is recommended to be done at least once a week. Patients will also be instructed to self-assess blood glucose levels whenever they experience any illnesses (eg, cold, flu), or symptoms of hyperglycemia or hypoglycemia. Note that the SMBG measurements obtained with glucose meters are displayed as plasma glucose concentration. The SMBGs  $\leq 70$  mg/dL will be reported on the hypoglycemia specific electronic case report form page.
- g* The 12-lead ECG recordings should be obtained prior to IMP administration. The ECG will be evaluated as "normal" or "abnormal".
- h* All laboratory assessments occur prior to dose of double-blind IMP and NIMP.
- i* The FPG is performed in fasting status, ie, without any food intake (except for water) for at least 8 hours.
- j* The FSH and serum estradiol is performed in all women at Screening to confirm menopausal status as needed.
- k* Markers of bone turnover include: markers of bone resorption (serum NTX, serum  $\beta$ -CTX-1) and bone formation (serum P1NP and osteocalcin).
- l* Markers of calcium metabolism include: serum and urinary calcium (adjusted for creatinine), serum 25-hydroxyvitamin D, serum 1,25-dihydroxyvitamin D, serum and urinary phosphorus (adjusted for serum phosphorus, and creatinine), serum and urinary magnesium (adjusted for serum magnesium and creatinine), serum iPTH.
- m* 24-hour urine samples for calcium, phosphorus, and magnesium will be collected at Weeks 0, 26, 52, and 104. Patients will be instructed to initiate the 24-hour urine collection on the day before the visits. In exceptional situations, the 24-hour urine collection can be done up to 2 days maximum prior to or after the visit, and the specimen should be sent to the study site as soon as possible.

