#### **9.1.4 Assessment methods of efficacy endpoints**

##### **9.1.4.1 Hemoglobin A1c**

Hemoglobin A1c will be assessed at Screening (Visit 1), Baseline (Visit 3), Week 12 (Visit 6), and Week 26 (Visit 8), Week 52 (Visit 10), Week 86 (Visit 12), and Week 104 (Visit 13) and measured by a certified Level I “National Glycohemoglobin Standardization Program” Central Laboratory.

If a patient needs to receive rescue antidiabetic medication, assessment of HbA1c should be performed before the introduction of the rescue therapy.

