#### 10.1.1.1.1 Screening Visit, Visit 1 (Week -4)

The following procedures/assessments will be performed at Visit 1 (Week -4):

- Obtain informed consent:
  - The patient will receive verbal information concerning the aims and methods of the study, its constraints and risks, and the study duration. Written information will be provided to the patient. Written informed consent must be signed by the patient and Investigator prior to any investigations.
  - 
- IRT notification (allocation of ID, registration of Screening).
- Assessment of inclusion/exclusion criteria.
- Collection of demographic data (age, gender, race, and ethnic origin).
- Assessment of the patient's medical and surgical history, including history, treatment and complications (eye, kidney, history of smoking/tobacco use, history of alcohol, and history of amputation events, etc) of T2D.
- Concomitant medication and medication history, including any prior medications for T2D.
- Measurement of BW and height.
- Complete physical examination including vital signs (SBP and DBP, HR, temperature, and respiratory rate) (see [Appendix C](#) for details).
- The following laboratory testing (by the central laboratory):
  - Serum 25-hydroxyvitamin D.

- HbA1c.
- Serum FSH and estradiol (for documentation of menopausal status).
- Clinical chemistry (including amylase, lipase) and hematology.
- AEs/SAEs/AESI/EOSI and hypoglycemia (if any) are reported.
- Urinalysis (dipstick and microscopy).
- Patients will be instructed to return to the site in the fasting state for Visit 3 (Week 0).

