Categorical endpoint of HbA1c $<$ 7% at week 26 will be analyzed using a Cochran-Mantel-Haenszel (CMH) method stratified by randomization stratum of HbA1c (\leq 8.5%, $>$ 8.5%), and randomization stratum of sex (male, female). Proportion of HbA1c responders in each treatment group will be provided with the difference between each sotagliflozin group and placebo group and their associated 2-sided 95% CI. To determine whether a patient is HbA1c responder or not, all measurements at week 26 will be used regardless of discontinuation of IMP or initiation of rescue medication. Patients with no HbA1c measurement at week 26 will be treated as non-responders. Summary tables and graphs will be provided by treatment group at scheduled visit.

For between-group comparison for HbA1c $<$ 7% responder analysis, a sensitivity analysis will be performed by excluding patients with baseline HbA1c $<$ 7% using the same CMH test mentioned above. Similarly, by-visit summary based on above subset of patients may be provided.

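### If the patient has eaten before the Week 26 visit, Protocol 10.1 defers the HbA1c draw along with the fasting tests: a small, avoidable risk to the primary endpoint

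*Protocol*

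**What the plan says.** Protocol 10.1 asks for fasting arrival at Visits 1, 3, 4, 5, 6, 8, 10, 12, 13 and 14, unless the investigator instructs otherwise. A Note deals with the patient who has eaten: "If the patient is not fasting at the visits specified above, the blood sample will not be collected", and then "a new appointment should be given to the patient for the following day if possible, with instruction to be fasted". Procedures other than the blood draw may go ahead. All laboratory sampling is to precede that day's IMP and NIMP.

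Where the protocol ties fasting to a particular test, the test is FPG. Footnote i of the flow chart (Protocol 1.2) reads "The FPG is performed in fasting status, ie, without any food intake (except for water) for at least 8 hours", and Protocol 9.1.4.3 repeats the condition. The flow chart also has a row for fasting lipids. The HbA1c row carries no fasting footnote. Protocol 9.1.4.1 opens with "Hemoglobin A1c will be assessed at Screening (Visit 1), Baseline (Visit 3), Week 12 (Visit 6), and Week 26 (Visit 8" and goes on to Weeks 52, 86 and 104 and the laboratory, without mentioning fasting.

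The SAP decides what happens when the value is absent:

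- **Substitution (2.5.4).** An unscheduled measurement may stand in for Week 26 if it falls on Days 154 to 227. Local laboratory results are not used for efficacy.
- **Primary endpoint (2.4.4.1).** A value still missing is imputed from same-arm patients who stopped IMP early but were measured. If any arm has fewer than 5 such patients, a washout method based on placebo is used.
- **Responder endpoint (2.4.4.2).** "Patients with no HbA1c measurement at week 26 will be treated as non-responders".

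**The concern.** The Note treats the blood sample as one unit. Protocol 9.4 describes HbA1c as an index of glycemia over roughly the preceding 120 days, so a meal that morning is no evident reason to refuse the tube that carries the primary endpoint. Protocol 6.2.2 asks sites to bring patients who stopped IMP back at Week 26 and stresses the HbA1c measurement. Under the Note, such a patient who has eaten leaves without it.

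If the redraw never happens, a patient who is still taking IMP, and could have been measured, is handled statistically like someone who stopped IMP or took placebo. That pulls the treatment difference toward zero, and the missingness was avoidable.

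**Working it through.** **Step 1: is there another scheduled HbA1c in the Week 26 window?** HbA1c is scheduled on Day 84 (Week 12), Day 182 (Week 26) and Day 364 (Week 52). The window runs from 182 − 154 = 28 days before the target to 227 − 182 = 45 days after it. Day 84 is 154 − 84 = 70 days before the window opens, and Day 364 is 364 − 227 = 137 days after it closes. Weeks 18 and 39 have no HbA1c. The only possible substitutes are the rebooked draw or an unscheduled central-laboratory value.

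**Step 2: how easily is a deferred sample recovered?** Visit 8 has a window of ±3 days, Days 179 to 185, so a next-day return from an on-time visit is Day 183 and within it. Any later central redraw up to Day 227 is still usable under SAP 2.5.4. Permanent loss therefore needs both a missed return and no other central HbA1c in the window.

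**Step 3: reproduce the plan's power.** Inputs from Protocol 11.1: n = 120 per arm, difference Δ = 0.6, SD = 1.2, two-sided α = 0.05. No missing-data allowance is stated for HbA1c; the 30% there is for BMD.

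Power = Φ(Δ / (SD·√(2/n)) − 1.96) = Φ(0.6 / (1.2·√(2/120)) − 1.96) = Φ(3.873 − 1.96) = 0.972. The noncentral t with 238 degrees of freedom gives 0.971. The stated 97% is reproduced.

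**Step 4: size of the effect under an assumed loss.** Let f be the share of Week 26 HbA1c values permanently lost per arm. The documents give no value, so f is an assumption. Three versions, same formula:

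- A: fewer values only, n = 120(1 − f), Δ = 0.6
- B: lost active-arm patients imputed with no drug effect, n = 120, Δ = 0.6(1 − f)
- C: both penalties together

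| f | Lost per arm (120f) | A | B | C |
|---|---|---|---|---|
| 1% | 1.2 | 97.1% | 97.0% | 96.8% |
| 2% | 2.4 | 97.0% | 96.7% | 96.4% |
| 5% | 6 | 96.5% | 95.7% | 94.8% |
| 10% | 12 | 95.7% | 93.7% | 91.1% |

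Under B the planned difference shrinks by 0.02 × 0.6 = 0.012 to 0.05 × 0.6 = 0.03 percentage points for f of 2% to 5%. B and C are pessimistic for the SAP's first-choice method, which borrows from same-arm patients and need not imply zero effect. They are closer to the washout back-up.

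**Step 5: responder endpoint.** Lost patients stay in the denominator as non-responders. If loss is equal across arms and unrelated to response, each proportion, and so the difference between arms, is multiplied by (1 − f). At f of 2% to 5% the difference shrinks by 2% to 5% of itself.

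**The case against.** The strongest reply is that the Note postpones the sample and does not cancel it. The new appointment is to be given, and the qualifier about possibility most naturally concerns next-day timing. Protocol 10.1 also allows extra visits at any time and lets the investigator vary the fasting instruction. With the visit window and the SAP window, there are several chances to recover the value. The bias runs toward no effect, so it cannot produce a false positive, and HbA1c below 7% is outside the testing hierarchy. All of this stands and makes the loss a residual risk. It does not remove the point. The windows help only if blood is drawn, the investigator's latitude concerns how the patient arrives, and the Note exempts no analyte.

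A second reply is that HbA1c's freedom from fasting is inferred from silence, and that no passage classifies bone markers, iPTH or vitamin D by fasting status. This stands in part. The inference for HbA1c is well supported, but the other analytes should be left to the laboratory manual, which is not among the documents. A single fasted redraw would also keep HbA1c and FPG on the same day, but I found no planned analysis that needs them paired.

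Four stronger readings are tempting but not supported:

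- **The rule itself loses the sample.** It does so only when the patient fails to return and nothing else falls in the window.
- **Visits 1 and 14 should leave the fasting list.** Neither has FPG or fasting lipids, and at Visit 1 "Written informed consent must be signed by the patient and Investigator prior to any investigations", so arrival fasted is expected before consent. But chemistry at both visits includes serum glucose (Protocol 9.2.1.4, Table 2), Protocol 8.3.1 refers to fasting glucose in plasma or serum, and the Visit 13 procedures repeat the fasting instruction for Visit 14.
- **Patients drop out of the responder analysis.** They are counted, as non-responders.
- **A few lost values could switch the primary imputation method.** This is possible in principle, because the threshold is 5 retrieved dropouts in any arm. The SAP says only that it expects few, so it cannot be sized.

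**Conclusion.** The point holds as a minor operational weakness. As written, Protocol 10.1 can turn a patient who attended Week 26 into a missing primary-endpoint value for a reason that the documents do not apply to HbA1c. At an assumed permanent loss of 2% to 5%, power stays between about 95% and 97%, against 97% planned, with the lower end resting on the pessimistic assumption of no drug effect in imputed patients. Nothing here supports a change to sample size or to the analysis. The case for acting is that the remedy is simple and the missingness is avoidable.

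**What to change.** Amend the Note in Protocol 10.1, and the laboratory manual to match, along these lines: *If the patient is not fasting, take HbA1c, and any other analyte that the laboratory manual classes as not requiring fasting, at this visit. Defer only FPG, fasting lipids and, where required, serum glucose to a fasted redraw, the next day if possible.* The HbA1c exception should apply at least at Weeks 12, 26, 52, 86 and 104. Keep the list of fasting visits as it is.

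The amended Note should also say how it fits with the requirement that samples precede that day's IMP and NIMP, since a patient who has eaten may already have dosed. The sponsor should settle that.

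The cost is a wording change and an occasional second venipuncture for patients who arrive having eaten. The SAP needs no change.
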